4.5.2 Management of specific toxicities

Overall, safety data available from completed, controlled and uncontrolled studies indicate that everolimus is generally well tolerated at weekly or daily dose schedules. The safety profile is characterized by manageable adverse events (AEs). These AEs are generally reversible and non-cumulative.

Adverse events most frequently observed with everolimus are rash, stomatitis /oral mucositis, non-infectious pneumonitis, fatigue, headache, anorexia, nausea, vomiting, diarrhea, and infections. Overall, the most frequently observed laboratory abnormalities include neutropenia, thrombocytopenia, hypercholesterolemia, and/or hypertriglyceridemia. The majority of these AEs have been of mild to moderate severity (NCI CTC grade 1-2). Recommendations for dose adjustments, should any of these treatment-related adverse events occur, are given in Table 4-1, 4-2, 4-3, 4-4, 4-5 and 4-6.

4.5.3 Management of infections

Everolimus has immunosuppressive properties and may predispose patients to bacterial, fungal, viral or protozoal infections, including infections with opportunistic pathogens. Localized and systemic infections, including pneumonia, other bacterial infections, invasive fungal infections, such as aspergillosis or candidiasis and viral infections including reactivation of hepatitis B virus, have been described in patients taking Everolimus. Some of these infections have been severe (e.g. leading to respiratory or hepatic failure) and occasionally have had a fatal outcome. Physicians and patients should be aware of the increased risk of infection with Everolimus. Treat pre-existing infections prior to starting treatment with Everolimus. While taking Everolimus, be vigilant for symptoms and signs of infection; if a diagnosis of infection is made, institute appropriate treatment promptly and consider interruption or discontinuation of Everolimus.

If a diagnosis of invasive systemic fungal infection is made, discontinue Everolimus and treat with appropriate antifungal therapy.

4.5.4 **Management of skin toxicity**

For patients with grade 1 toxicity, no specific supportive care is usually needed or indicated. Rash must be reported as an AE. Patients with grade 2 or higher toxicity may be treated with the following suggested supportive measures at the discretion of the investigator: oral minocycline, topical tetracycline, topical clindamycin, topical silver sulfadiazine, diphenhydramine, oral prednisolone (short course), topical corticosteroids, or pimecrolimus.

4.5.5 **Management of stomatitis / oral mucositis / mouth ulcers**

Patients with a clinical history of stomatitis/mucositis/mouth ulcers and those with gastrointestinal morbidity associated with mouth/dental infections, irritation of esophageal mucosa e.g. gastroesophageal reflux disease (GERD) and pre-existing stomatitis/mucositis must be monitored even more closely. Patients should be instructed to report the first onset of buccal mucosa irritation/reddening to their study physician immediately.

Stomatitis/oral mucositis/mouth ulcers due to Everolimus should be treated using local supportive care. Please note that investigators in earlier trials have described the oral toxicities associated with Everolimus as mouth ulcers, rather than mucositis or stomatitis. If your examination reveals mouth ulcers rather than a more general inflammation of the mouth, please classify the adverse event as such. Please follow the paradigm below for treatment of stomatitis/oral mucositis/mouth ulcers:

1. For mild toxicity (grade 1), use conservative measures such as non-alcoholic mouth wash or salt water (0.9%) mouth wash several times a day until resolution.
2. For more severe toxicity (grade 2 in which case patients have pain but are able to maintain adequate oral alimentation, or grade 3 in which case patients cannot maintain adequate oral alimentation), the suggested treatments are topical analgesic mouth treatments (i.e., local anesthetics such as, benzocaine, butyl aminobenzoate, tetracaine hydrochloride, menthol, or phenol) with or without topical corticosteroids, such as triamcinolone oral paste 0.1% (Kenalog in Orabase®).
3. Agents containing alcohol, hydrogen peroxide, iodine, and thyme derivatives may tend to worsen mouth ulcers. It is preferable to avoid these agents.
4. Antifungal agents should be avoided unless a fungal infection is diagnosed. In particular, systemic imidazole antifungal agents (ketoconazole, fluconazole, itraconazole, etc.) should be avoided in all patients due to

their strong inhibition of Everolimus metabolism, therefore leading to higher Everolimus exposures. Therefore, topical antifungal agents are preferred if an infection is diagnosed.

4.5.6 **Management of diarrhea**

Appearance of grade 1-2 diarrhea attributed to study drug toxicity may be treated with supportive care such as loperamide, initiated at the earliest onset at age and weight appropriate doses.

4.5.7 **Management of hyperlipidemia and hyperglycemia**

Treatment of hyperlipidemia should take into account the pre-treatment status and dietary habits of the patient. Grade 2 or higher hypercholesterolemia (>300 mg/dL or 7.75 mmol/L) or grade 2 hypertriglyceridemia or higher (>2.5 times upper normal limit) should be treated with lifestyle and dietary changes, in addition to an appropriate triglyceride-lowering medication approved for children, such as fish oil or fenofibrate.³¹

Hyperglycemia has been reported in clinical trials. Monitoring of fasting serum glucose is recommended prior to the start of Everolimus and periodically thereafter. Optimal glycemic control should be achieved before starting a patient on Everolimus.

4.5.8 **Management of non-infectious pneumonitis**

Non-infectious pneumonitis is a class effect of rapamycin derivatives. Cases of non-infectious pneumonitis (including interstitial lung disease) have also been described in patients taking Everolimus. Some of these have been severe and on rare occasions, a fatal outcome was observed.

- A diagnosis of non-infectious pneumonitis should be considered in patients presenting with non-specific respiratory signs and symptoms such as hypoxia, pleural effusion, cough or dyspnea, and in whom infectious, neoplastic and other non-medicinal causes have been excluded by means of appropriate investigations. Patients should be advised to report promptly any new or worsening respiratory symptoms.
- Patients who develop radiological changes suggestive of non-infectious pneumonitis and have few or no symptoms may continue Everolimus therapy without dose alteration.

Individuals participating in this trial will be routinely questioned as to the presence of new or changed pulmonary symptoms consistent with lung toxicity. In addition, pulmonary function tests (PFTs) can be conducted, if clinically indicated, to monitor for pneumonitis. If non-infectious pneumonitis develops, the guidelines in Table 4-3 should be followed. Consultation with a pulmonologist is recommended for any case of pneumonitis that develops during the study.

Table 4-3**Management of non-infectious pneumonitis**

Worst grade pneumonitis	Required investigations	Management of pneumonitis	Everolimus dose adjustment
Grade 1	CT scans with lung windows.	No specific therapy is required	No dose adjustment required. Initiate appropriate monitoring.
Grade 2	CT scan with lung windows. Consider pulmonary function testing includes: spirometry, DLCO, and room air O ₂ saturation at rest. Consider a bronchoscopy with biopsy and/or BAL. Monitoring at each visit until return to ≤ grade 1. Return to initial monitoring frequency if no recurrence.	Symptomatic only. Consider corticosteroids and/or other supportive therapy if symptoms are troublesome.	Rule out infection and consider interruption of Everolimus until symptoms improve to Grade ≤ 1. Re-initiate Everolimus at one dose level lower. Discontinue Everolimus if failure to recover within ≤ 28 days.
Grade 3	CT scan with lung windows and pulmonary function testing includes: spirometry, DLCO, and room air O ₂ saturation at rest. Monitoring at each visit until return to ≤ grade 1. Return to initial monitoring frequency if no recurrence. Bronchoscopy with biopsy and/or BAL is recommended.	Consider corticosteroids if infective origin is ruled out. Taper as medically indicated.	Rule out infection and interrupt Everolimus until symptoms improve to Grade ≤ 1. Consider re-initiating Everolimus at one dose level lower. Discontinue Everolimus if failure to recover within ≤ 28 days.
Grade 4	CT scan with lung windows and required pulmonary function testing, if possible, includes: spirometry, DLCO, and room air O ₂ saturation at rest. Monitoring at each visit until return to ≤ grade 1. Return to initial monitoring frequency if no recurrence. Bronchoscopy with biopsy and/or BAL is recommended if possible.	Consider corticosteroids if infective origin is ruled out. Taper as medically indicated.	Rule out infection and discontinue Everolimus.

4.5.9 Management of hepatitis reactivation / flare

Reactivation of Hepatitis B (HBV) has been observed in patients with cancer receiving chemotherapy.³² Sporadic cases of Hepatitis B reactivation have also been seen in this setting with everolimus. Use of antivirals during anti-cancer therapy has been shown to reduce the risk of Hepatitis B virus reactivation and associated morbidity and mortality.³³ A detailed assessment of Hepatitis B/C medical history and risk factors must be done for all patients at screening, with testing performed prior to the first dose of everolimus.

4.5.10 Monitoring and prophylactic treatment for hepatitis B reactivation.

Table 4-4 provides details for monitoring and prophylactic therapy according to the screening results of viral load and serologic markers testing.

Table 4-4 Action to be taken based on screening hepatitis B results

Test	Result	Result	Result	Result	Result
HBV-DNA	+	+ or -	-	-	-
HBsAg	+ or -	+	-	-	-
HBsAb	+ or -	+ or -	+ and no prior HBV vaccination	+ or -	- or + with prior HBV vaccination
HBcAb	+ or -	+ or -	+ or -	+	-
Recommendation	Prophylaxis treatment should be started 1-2 weeks prior to first dose of Everolimus Monitor HBV-DNA approximately every 4-8 weeks		No prophylaxis Monitor HBV-DNA approximately every 3-4 weeks		No specific action

Antiviral prophylaxis therapy should continue for at least 4 weeks after last dose of Everolimus. For HBV reactivation definition and management guidelines, see Table 4-5.

Table 4-5 Guidelines for the management of hepatitis B reactivation

HBV reactivation (with or without clinical signs and symptoms)*	
For patients with baseline results: Positive HBV-DNA OR positive HBsAg ----- reactivation is defined as: [Increase of 1 log in HBV-DNA relative to baseline HBV-DNA value OR new appearance of measurable HBV-DNA]	Treat: Start a second antiviral medication AND Interrupt Everolimus administration until resolution: • \leq baseline HBV-DNA levels If resolution occurs within \leq 28 days, Everolimus should be re-started at one dose lower, if available. If the patient is already receiving the lowest dose of Everolimus according to the protocol, the patient should restart at the same dose after resolution. Both antiviral therapies should continue at least 4 weeks after last dose of Everolimus. If resolution occurs $>$ 28 days Patients should discontinue Everolimus but continue both antiviral therapies at least 4 weeks after last dose of Everolimus.
For patients with baseline results: Negative HBV-DNA and HBsAg AND [Positive HBsAb (with no prior history of vaccination against HBV), OR positive HBcAb] ----- Reactivation is defined as: New appearance of measurable HBV-DNA	Treat : Start first antiviral medication AND Interrupt Everolimus administration until resolution: • \leq undetectable (negative) HBV-DNA levels If resolution occurs within \leq 28 days, Everolimus should be re-started at one dose lower, if available . If the patient is already receiving the lowest dose of Everolimus according to the protocol, the patient should restart at the same dose after resolution. Antiviral therapy should continue at least 4 weeks after last dose of Everolimus. If resolution occurs $>$ 28 days Patients should discontinue Everolimus but continue antiviral therapy at least 4 weeks after last dose of Everolimus.

* All reactivations of HBV are to be recorded as grade 3 (e.g. CTCAE Version 4.03 - Investigations/Other: Viral Reactivation), unless considered life threatening by the investigator, in which case they should be recorded as grade 4. Date of viral reactivation is the date on which the rise or reappearance of HBV-DNA was recorded.

4.5.11 Monitoring for hepatitis C flare

The following two categories of patients should be monitored every 4–8 weeks for HCV flare:

- Patients with detectable HCV RNA-PCR test at screening.
- Patients known to have a history of HCV infection, despite a negative viral load test at screening (including those that were treated and are considered 'cured')

For definitions of HCV flare and actions to be taken in the event of a flare, please refer to
Table 4-6.

Table 4-6**Guidelines for the management of hepatitis C flare**

Baseline results	HCV flare definition*	HCV flare management
Detectable HCV-RNA	> 2 log ₁₀ IU/mL increase in HCV-RNA AND ALT elevation > 5 x ULN or 3 x baseline level, whichever is higher.	Discontinue Everolimus
Knowledge of past hepatitis C infection with no detectable HCV-RNA	New appearance of detectable HCV-RNA AND ALT elevation > 5 x ULN or 3 x baseline level, whichever is higher.	Discontinue Everolimus

* All flares of HCV are to be recorded as grade 3 (e.g. CTCAE Version 4.03 - Investigations - Other: Viral Flare), unless considered life threatening by the investigator; in which case they should be recorded as grade 4. Date of viral flare is the date on which both the clinical criteria described above were met. (e.g., for a patient whose HCV-RNA increased by 2 logs on 01 JAN 2011 and whose ALT reached > 5 x ULN on 22 JAN 2011, the date of viral flare is 22 JAN 2011).

4.6 Concomitant Medications

Patients must be instructed not to take any medications (over-the-counter or other products) during the protocol treatment period without prior consultation with the investigator. The investigator should instruct the patient to notify the study site about any new medications he/she takes after the start of study drug. All medications (other than study drug) and significant non-drug therapies (including physical therapy and blood transfusions) taken within 28 days of starting study treatment through the 30-day safety follow up visit should be reported on the CRF.

4.6.1 Permitted concomitant therapy: Other than study medications, patients may take other supportive therapies as prescribed by their treating physician. Treatment with systemic anticancer agents (chemotherapy, hormone therapy, targeted or biologic agents) other than the protocol treatment is not permitted.

4.6.2 Cytochrome P450 and P-glycoprotein inhibitors/inducers/substrates: Everolimus is metabolized by CYP3A4 in the liver and to some extent in the intestinal wall. Therefore, the following are recommended:

- Co-administration with strong inhibitors of CYP3A4 (e.g., ketoconazole, itraconazole, ritonavir) or P-glycoprotein (PgP) inhibitor should be avoided.
- Co-administration with moderate CYP3A4 inhibitors (e.g., erythromycin, fluconazole) or PgP inhibitors should be used with caution. If a patient requires co-administration of moderate CYP3A4 inhibitors or PgP inhibitors, reduce the dose of everolimus. Additional dose reductions to every other day may be required to manage toxicities. If the inhibitor is discontinued, the Everolimus dose should be returned to the dose used

prior to initiation of the moderate CYP3A4/PgP inhibitor after a washout period of 2 to 3 days.

- Grapefruit or citrus juices affect P450 and PgP activity. Concomitant use should be avoided.
- Concomitant use of medications known to have inhibition or induction of CYP3A enzymes is strongly discouraged and should be discussed with the study chair. If patients begin therapy with strong CYP3A inducers (i.e., phenytoin, carbamazepine, rifampin, rifabutin, phenobarbital, St. John's wort), perform Everolimus trough concentration in 2 weeks. Enzyme induction usually occurs within 2 weeks.
- For patients with low Everolimus trough concentrations (< 5 ng/ml), increase doses by 33% and repeat trough concentration in 2 weeks.
- For patients with elevated Everolimus trough levels (>15 ng/ml), decrease dose by 25% and repeat trough concentration in 2 weeks.
- Co-administration with strong inducers or inhibitors of CYP3A4 is strongly discouraged and should be discussed with the study chair. If a patient requires co-administration of strong CYP3A4 inducers (i.e., phenytoin, carbamazepine, rifampin, rifabutin, phenobarbital, St. John's wort), an increase in the dose of Everolimus may be necessary. Enzyme induction usually occurs within 2 weeks; therefore Everolimus dose should be increased by one increment 7 days after the start of the inducer therapy. If no safety concerns are seen within the next 7 days, the dose can be increased again one additional increment up to a maximum of twice the daily dose used prior to initiation of the strong CYP3A4 inducer.
- This dose adjustment of Everolimus is intended to achieve similar AUC to the range observed without inducers. However, there are no clinical data with this dose adjustment in patients receiving strong CYP3A4 inducers. If the strong inducer is discontinued the Everolimus dose should be returned to the dose used prior to initiation of the strong CYP3A4/PgP inducer. Please refer to Table 4-7 listing relevant inducers and inhibitors of CYP3A and Table 4-8 for a list of relevant substrates, inducers, and inhibitors of PgP.

Table 4-7
isoenzyme CYP3A

Clinically relevant drug interactions: inducers, and inhibitors of

Inducers:

carbamazepine, glucocorticoids, modafinil, oxcarbazepine, phenobarbital, phenytoin, pioglitazone, rifabutin, rifampin, St. John's wort, troglitazone, efavirenz, nevirapine, topiramate, avasimibe, bosentan, etravirine, naftcillin, ritonavir, talviraline (not available in US market), tipranavir, amprenavir, aprepitant, armodafinil (R-modafinil), dexamethasone, nevirapine, prednisone, pleconaril (not available in US market), rufinamide

Inhibitors:

Strong inhibitors:

clarithromycin, conivaptan, indinavir, itraconazole, ketoconazole, lopinavir, mibefradil, nefazodone, nelfinavir, ritonavir, saquinavir, telithromycin, troleandomycin, voriconazole, tipranavir, elvitegravir, Posaconazole ([Krishna et al 2009](#))

Moderate inhibitors:

aprepitant, atazanavir, casopitant, cimetidine, ciprofloxacin, darunavir, diltiazem, erythromycin, fluconazole, grapefruit juice (citrus paradisi fruit juice), imatinib, tofisopam, verapamil, amprenavir, fosamprenavir, dronedarone

Table 4-8 Clinically relevant drug interactions: substrates, inducers, inhibitors of PgP and PgP/CYP3A dual inhibitors

Substrates:
digoxin, fexofenadine, indinavir, vincristine, colchicine, topotecan, paclitaxel
Inducers:
rifampin, St John's wort
PgP Inhibitors and PgP/CYP3A Dual Inhibitors:
amiodarone, captopril, carvedilol, clarithromycin, conivaptan, diltiazem, dronedarone, elacridar, erythromycin, felodipine, fexofenadine, ginkgo (ginkgo biloba), indinavir, itraconazole, lopinavir, mibepradil, milk thistle (silybum marianum), nifedipine, nitrendipine, quercetin, quinidine, ranolazine, ritonavir, saquinavir, Schisandra chinensis, St John's wort (hypericum perforatum), talinolol, telmisartan, tipranavir, valspar, verapamil
Reference: Internal Clinical Pharmacology Drug-drug interaction (DDI) memo, updated Oct. 2, 2011, which summarizes DDI data from three sources including the FDA's "Guidance for Industry, Drug Interaction Studies", the University of Washington's Drug Interaction Database, and Indiana University School of Medicine's Drug Interaction Table.

4.6.3 **Vaccinations:** Immunosuppressants may affect the response to vaccination and vaccination during treatment with Everolimus may therefore be less effective. The use of live vaccines should be avoided during treatment with Everolimus. Examples of live vaccines are: intranasal influenza, measles, mumps, rubella, oral polio, BCG, yellow fever, varicella, and TY21a typhoid vaccines.

4.6.4 **Wound healing complications:** Impaired wound healing is a class effect of rapamycin derivatives, including everolimus. Caution should therefore be exercised with the use of Afinitor in the peri-surgical period.

4.6.5 **Prohibited concomitant therapy** Anti-neoplastic therapies: Treatment with systemic anticancer agents (chemotherapy, hormone therapy, targeted or biologic agents) other than the protocol treatment is not permitted until disease progression is documented per RECIST. Palliative radiotherapy or surgery is not allowed.

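### Section 4.6.2 both rules out PgP inhibitors and allows them with caution, and for St John's wort it supports opposite everolimus dose changes

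*Combined protocol and SAP*

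**What the plan says.** Section 4.6.2 opens with two bullets on inhibitors. The first covers strong CYP3A4 inhibitors, naming ketoconazole, itraconazole and ritonavir, and extends to PgP inhibitors: co-administration with the former "or P-glycoprotein (PgP) inhibitor should be avoided". The second reads "Co-administration with moderate CYP3A4 inhibitors (e.g., erythromycin, fluconazole) or PgP inhibitors should be used with caution", followed by "If a patient requires co-administration of moderate CYP3A4 inhibitors or PgP inhibitors, reduce the dose of everolimus".

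Later in the same section, if a patient requires "strong CYP3A4 inducers (i.e., phenytoin, carbamazepine, rifampin, rifabutin, phenobarbital, St. John's wort), an increase in the dose of Everolimus may be necessary"; "therefore Everolimus dose should be increased by one increment 7 days after the start of the inducer therapy". A second increment is possible after a further 7 days without safety concerns, with a ceiling of twice the dose used before the inducer.

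Table 4-7 lists CYP3A inducers without grading them and splits CYP3A inhibitors into strong and moderate. Table 4-8 gives PgP inducers and one ungraded list of PgP inhibitors and PgP/CYP3A dual inhibitors. St John's wort is among the PgP inducers and again in the inhibitor list, where the entry begins "St John's wort (hypericum perforatum".

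Section 4.5.5, on mouth ulcers and mucositis, says that "systemic imidazole antifungal agents (ketoconazole, fluconazole, itraconazole, etc.) should be avoided in all patients" and gives strong inhibition of everolimus metabolism as the reason.

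**The concern.** Everolimus exposure in this trial is steered to a trough of 5 to 15 ng/mL, and Section 1.4 presents trough monitoring as the safeguard against excessive exposure. Co-medication rules that change the dose ahead of a trough therefore need to be unambiguous.

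As written, a site treating a child who needs a PgP inhibitor cannot tell whether the drug is ruled out or acceptable with a reduced everolimus dose. For St John's wort, two sites could each follow the protocol and move the dose in opposite directions. The fluconazole wording is likely to be met in practice: Section 4.5.2 puts stomatitis and infections among the most frequent adverse events, and 4.5.5 is where a clinician treating mouth lesions would look. At stake are patient safety and, in a trial of 18 patients, differences in exposure that depend on which sentence a site happens to apply.

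**Working it through.** The plan states no figure to reproduce. The check sets the instructions in 4.6.2 against the drug lists in Tables 4-7 and 4-8.

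**1. PgP inhibitors: two rules, one list.** The inhibitor list in Table 4-8 has 31 entries. Compared with Table 4-7:
- 9 are also strong CYP3A inhibitors: clarithromycin, conivaptan, indinavir, itraconazole, lopinavir, mibefradil, ritonavir, saquinavir, tipranavir.
- 4 are also moderate CYP3A inhibitors: diltiazem, dronedarone, erythromycin, verapamil.
- 31 − 9 − 4 = 18 are neither.

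For the 18, only the PgP wording places them, and it places them under both bullets. The 4 moderate inhibitors belong to the caution bullet on CYP3A4 grounds and to the avoid bullet on PgP grounds. The 9 strong inhibitors are to be avoided on CYP3A4 grounds, yet are allowed with caution on PgP grounds. The section's own examples cross over: erythromycin is the second bullet's example and is on the list that the first bullet rules out, while itraconazole and ritonavir are first-bullet examples and are on the list that the second bullet admits.

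**2. Dose direction.**
- Increase set: the six named inducers (phenytoin, carbamazepine, rifampin, rifabutin, phenobarbital, St John's wort).
- Reduce set: the moderate inhibitors of Table 4-7 plus the PgP inhibitor list of Table 4-8.
- Overlap: St John's wort only, 1 of 6.

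**3. Dual listing.** Drugs that appear as an inducer in either table and as an inhibitor in either table number 5: St John's wort, ritonavir, tipranavir, aprepitant and amprenavir. In Table 4-7, ritonavir and tipranavir are inducers and strong inhibitors; aprepitant and amprenavir are inducers and moderate inhibitors. All 5 fall in the reduce set. Only St John's wort is in the increase set, so 5 − 1 = 4 have a double listing without two opposite dose instructions.

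**4. Timing for St John's wort.** The first increase comes at day 7. Section 5.2.4 puts the trough at 2 weeks ± 4 days after an inducer or inhibitor is started, that is 14 ± 4, or days 10 to 18. The first step therefore precedes the earliest scheduled trough by 10 − 7 = 3 days. The second step, at about 7 + 7 = day 14, falls inside the window, so a trough may or may not be available by then.

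**5. Fluconazole.** Section 4.5.5 groups it with ketoconazole and itraconazole, to be avoided in every patient because of strong inhibition. Section 4.6.2 names it as a moderate inhibitor usable with caution, and Table 4-7 lists it as moderate. Both the class and the action differ.

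**The case against.** Several points on the other side are sound.

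- The bullets in 4.6.2 are introduced as recommendations, apply when a patient requires the drug, and first describe the increase as something that may be needed. This softens them, but the sentences that follow still tell the site to reduce or to increase.
- Strong and moderate could be read as grading PgP inhibitors too, which would separate the two bullets. Table 4-8 has no such grading, so a site could not apply that reading.
- The tables describe drug properties, and a drug can have more than one. Double listing is not in itself an error, and its pharmacological correctness cannot be judged from these documents. What is missing is a statement of which listing governs the action.
- The named-drug instruction for St John's wort might be taken to override its place in a general list. The protocol does not say so.
- Section 4.5.5 makes an exception for diagnosed fungal infection and prefers topical agents, so avoiding fluconazole by default and using it cautiously when required could coexist. The blanket wording and the different strength class still do not match.
- Patients must consult the investigator before taking any medication, CYP3A inhibitors and inducers are to be discussed with the study chair, the Appendix I checklist treats their use as an exclusion, and troughs follow both a change of interacting drug and a dose change. These lower the risk. None says which rule applies.

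A reader might infer more than the text supports. It does not give opposite dose directions for all five dual-listed drugs: the increase instruction is confined to six named inducers, and Table 4-7 does not grade inducers, so nothing brings the other four under it. Nor does it withhold everolimus: the word avoided applies to the co-medication. Nor does it call for doubling before any trough could be drawn: twice the prior dose is a ceiling, and the second step falls within the trough window.

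**Conclusion.** The inconsistency is real and the section is wrong as written, within these limits:

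- two incompatible rules for PgP inhibitors, covering all 31 entries of the Table 4-8 inhibitor list;
- opposite dose directions for exactly one drug, St John's wort, with the first increase due before the trough window opens;
- four further drugs listed as both inducer and inhibitor with no governing listing stated;
- one mismatch of class and action, for fluconazole.

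The counts assume that the tables were read correctly from the PDF and that the differently spelled mibefradil entries in the two tables are the same drug. How many patients would be affected cannot be estimated, because the documents give no expected use of these co-medications. The point concerns clinical management and internal consistency. It does not bear on the two-stage design figures in Section 9.2, and no effect on the primary endpoint has been shown. No view is taken on which dose or rule is right.

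**What to change.** Reconcile the first two bullets of 4.6.2 so that PgP inhibitors fall under one rule, or under two rules that Table 4-8 lets a site tell apart. State which instruction governs for St John's wort, and which listing governs for ritonavir, tipranavir, aprepitant and amprenavir. Make 4.5.5 agree with 4.6.2 and Table 4-7 on fluconazole. The sponsor decides the content.

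The cost is an amendment to protocol wording and two tables, with the IRB approval that Section 10.7 requires. Sample size, visit schedule and analyses do not change.

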- Everolimus trough levels will be assessed 2 weeks (+/- 4 days) after starting drug. If the level is outside of the target range, then the dose should be adjusted to achieve a trough level of 5 – 15 ng/ml. Trough levels should be assessed within one hour before taking the daily dose.
- Whenever any dose adjustment of Everolimus occurs, trough levels should be reassessed two weeks (+/- 4 days) following the adjustment to ensure that the new dose achieves the target drug trough level of 5-15 ng/ml.
- Furthermore, Everolimus trough levels should be assessed 2 weeks (+/- 4 days) following the starting, ending, or changing of the dose of inducers or inhibitors of CYP3A4 or P-glycoprotein.

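### Section 4.6.2 gives two unreconciled dose-change instructions for the same six strong CYP3A inducers, one tied to a 2-week trough and one to the calendar, with an undefined 'increment'

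*Combined protocol and SAP*

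**What the plan says.** Section 4.6.2 deals twice with phenytoin, carbamazepine, rifampin, rifabutin, phenobarbital and St. John's wort.

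- **Trough instruction.** If a patient begins one of these drugs: "perform Everolimus trough concentration in 2 weeks. Enzyme induction usually occurs within 2 weeks". The next two bullets give the response: below 5 ng/mL, "increase doses by 33% and repeat trough concentration in 2 weeks"; above 15 ng/mL, "decrease dose by 25% and repeat trough concentration in 2 weeks".
- **Calendar instruction.** A later bullet with the identical drug list says an increase may be needed and then directs: "Everolimus dose should be increased by one increment 7 days after the start of the inducer therapy". It then adds an optional second step: "If no safety concerns are seen within the next 7 days, the dose can be increased again one additional increment". The total is limited to double what the child took before the inducer. The following bullet acknowledges that no clinical data support this adjustment in patients on strong inducers.

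Both instructions strongly discourage such co-medication and refer the case to the study chair.

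Elsewhere, section 4.5.1.1 requires a trough 2 weeks (+/- 4 days) after any dose change and after an inducer is started. Section 5.2.4 requires the same: "Whenever any dose adjustment of Everolimus occurs, trough levels should be reassessed two weeks (+/- 4 days) following the adjustment". Section 4.5.1.2 titrates an out-of-range trough in 2 mg steps and separately lists dose levels in mg/m².

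**The concern.** Both instructions argue from the same premise, that induction usually develops within 2 weeks, but reach different actions. On day 7 one directs an increase and the other directs nothing until a trough is drawn. The text does not say which governs or how they combine. The term 'increment' is not tied to any of the three step sizes that the protocol uses.

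Section 1.4 gives trough monitoring as the means of preventing excessive exposure. The calendar instruction allows two increases before the first has had the re-check that 5.2.4 requires. Two clinicians who each follow the text could therefore have the same child on different doses at day 14. The trial is multi-center with at most 18 patients in its two-stage design, so a dosing rule that reads two ways should be settled in writing.

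**Working it through.** The plan states no resulting dose for this situation, so there is no figure to reproduce. The check sets out the timing and then the dose arithmetic.

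**Timing, counted from inducer start (day 0)**

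- Trough due after inducer start (4.5.1.1, 5.2.4): 14 +/- 4 = days 10 to 18.
- Gap from a day-7 increase to that trough: 10 - 7 = 3 days to 18 - 7 = 11 days.
- Re-check due after the day-7 increase (5.2.4): 7 + 14 +/- 4 = days 17 to 25.
- Optional second increase: 7 + 7 = about day 14, before day 17.
- Re-check due after a day-14 increase: 14 + 14 +/- 4 = days 24 to 32.

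One draw can meet both of the first two requirements only on days 17 to 18, and it is a clean check of the first increase only if the second has not been taken.

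**Dose at day 14**

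Inputs: starting dose 4.5 mg/m² (4.1); tablets of 2, 3 and 5 mg (4.3.3); the cap of twice the earlier dose (4.6.2); steps of 2 mg or of dose levels 4.5, 5.2 and 6 mg/m² (4.5.1.2), or of 33% (4.6.2).

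Assumptions: body surface area (BSA) 0.5 to 2.0 m²; the child is at 4.5 mg/m² when the inducer starts; every dose is rounded to the nearest whole mg that the tablets can make; both calendar steps are taken.

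Formulas, with D the earlier dose:
- 2 mg reading: min(D + 4, 2D)
- level reading: 6 × BSA, rounded
- 33% reading: min(D × 1.33², 2D), rounded; 1.33² = 1.77
- trough instruction: D until a trough result, then D × 1.33, rounded, if it is low

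| BSA (m²) | D (mg) | 2 mg steps | Level steps | 33% steps | Trough instruction after one low trough |
|---|---|---|---|---|---|
| 0.5 | 2 | 4 (2.0x) | 3 (1.5x) | 4 (2.0x) | 3 |
| 0.6 | 3 | 6, capped (2.0x) | 4 (1.33x) | 5 (1.67x) | 4 |
| 0.8 | 4 | 8 (2.0x) | 5 (1.25x) | 7 (1.75x) | 5 |
| 1.2 | 5 | 9 (1.8x) | 7 (1.4x) | 9 (1.8x) | 7 |
| 1.5 | 7 | 11 (1.57x) | 9 (1.29x) | 12 (1.71x) | 9 |
| 2.0 | 9 | 13 (1.44x) | 12 (1.33x) | 16 (1.78x) | 12 |

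The calendar instruction therefore gives about 1.25 to 2.0 times D, against 1.0 times D under the trough instruction before any trough-driven change. Unrounded, the level reading is 6.0/4.5 = 1.33 times. At exactly 1.0 m² the 4.5 mg dose is a rounding tie: the level reading gives 6/4 = 1.5 times from 4 mg and 6/5 = 1.2 times from 5 mg.

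**After one low trough**

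In the table, calendar dose divided by trough-instruction dose is:
- level reading: 1.0 in every row (unrounded 1.333 against 1.33)
- 2 mg reading: 13/12 = 1.08 to 8/5 = 1.6
- 33% reading: 5/4 = 1.25 to 7/5 = 1.4

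**Step size for the same out-of-range trough**

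Section 4.5.1.2 moves by 2 mg; 4.6.2 moves by +33% or -25%, and its wording does not limit those steps to patients on interacting drugs. Upward steps are equal only at 2/0.33 = 6.1 mg and downward steps only at 2/0.25 = 8 mg. From 4 mg, a low trough leads to 6 mg under 4.5.1.2 and to 5.3 mg, rounded to 5 mg, under 4.6.2.

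**The case against.** The strongest reply is that the bullets are uncoordinated, not contradictory. The trough bullet never says to wait or to hold the dose, so a site could raise the dose at day 7 and still draw the 2-week trough. That is right, and a reader who infers that the two cannot both be followed goes further than the text. What remains is that the trough so drawn comes too early to serve as the re-check in 5.2.4, unless it falls on days 17 to 18 and no second step was taken.

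Nor does the calendar instruction dispense with troughs. Sections 4.5.1.1 and 5.2.4 still require them, including one after each adjustment. The increases are not conditional on a trough; they are not unmonitored. The second step is optional and depends on safety, and the whole list in 4.6.2 is introduced as recommendations.

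Three further inferences fail:
- **Broken cap.** A child on 3 mg given two 2 mg steps would reach 7 mg, but the cap sits in the same sentence and limits the second step to 6 mg. The rule is not broken.
- **Excess over the 5 mg/m² maximum in 1.4.** That figure is not a like-for-like comparator under induction. Section 4.6.2 aims at similar AUC, and 4.5.1.2 already lists a 6 mg/m² level.
- **Different doses by site.** Both instructions send the case to one study chair. Variation is possible, but the documents do not state it.

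Eligibility also limits the problem. Section 3.2.2 discourages strong inducers and calls the listed drugs prohibited, and the Appendix I checklist lists inducer use as an exclusion. The case is therefore mainly a drug started on study. Referral to the chair helps, but it supplies neither a written precedence nor a definition of the increment.

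**Conclusion.** The point holds as an unreconciled pair of dosing instructions. Followed as written, they give 1.0 times or about 1.25 to 2.0 times the earlier dose at day 14. The range depends on what an increment is, on both calendar steps being taken and on the rounding assumed. On the level reading the gap can close after one low trough; on the other two readings part of it stays. The different step sizes in 4.5.1.2 and 4.6.2 for the same trough are a related inconsistency.

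A reader might infer that this undermines the trial's response and safety results. The documents do not support that: the analyses in section 9.3 do not use trough values, only children who start a discouraged drug are affected, and their number is not given. This is a safety-relevant wording conflict of unknown frequency. Nothing here implies that either instruction is the right one.

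**What to change.** Amend section 4.6.2 so that it states which instruction governs strong inducers, or how the two combine, and make it agree with 4.5.1.2 on step size and with 5.2.4 on trough timing. Define 'increment' wherever the term is kept. State that the trough used to judge a new dose is timed from the last dose change, as 5.2.4 already requires. The choice of rule and step belongs to the sponsor.

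The cost is a wording amendment with the IRB approval that section 10.7 requires. It needs no troughs beyond those that 4.5.1.1 and 5.2.4 already call for.
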